11.2. CR Rate and Toxicity Monitoring

Complete response rate and toxicity will be monitored simultaneously using the Bayesian approach of Thall, Simon, Estey (1995, 1996) and the extension by Thall and Sung (1998). This regimen of the experimental treatment will be considered worthy of further investigation if it elicits an increase in CRR to 20% with acceptable toxicity. A toxicity rate greater than 30% is considered unacceptable. Thus, a beta (20, 80) and beta (0.4, 1.6) priors were assumed for the standard treatment response distribution and experimental treatment response prior distribution, respectively. In addition, a beta (30, 70) and beta (0.6, 1.4) priors were assumed for the standard treatment toxicity rate and experimental treatment toxicity prior distribution, respectively. Interim monitoring rules, assuming the prior distributions, were constructed that meet the following two conditions,

- 1) $\Pr(\theta_{S, \text{Toxicity}} < \theta_{E, \text{Toxicity}} | \text{data}) > 0.975$ and,
- 2) $\Pr(\theta_{E, \text{CR}} > \theta_{S, \text{CR}} | \text{data}) < 0.025$

Where $\theta_{E, \text{Toxicity}}$ and $\theta_{E, \text{CRR}}$ are the toxicity and response rates for the experimental treatment, and $\theta_{S, \text{Toxicity}}$ and $\theta_{S, \text{CRR}}$ are the toxicity and response rates for the standard treatment respectively. The first rule provides for stopping the study if excessive toxicity is highly probable (i.e., probability >97.5%) for the experimental treatment. The second condition will stop the study early if the data suggest that it is unlikely (i.e., probability < 2.5%) that CR rate of the experimental treatment is 20%. Assuming the minimum number of patients is 5, the maximum number of patients is 80 and the cohort size is 5. Multc Lean Desktop (version 2.1.0) was used to generate the toxicity and futility stopping boundaries and the OC table (Table 4). The monitoring rule for the toxicity rate, based on these assumptions and monitoring conditions above is in Table 2. Toxicity is defined as grade 3 or higher drug-related non-hematologic toxicity during the first cycle. For example, accrual will cease if 5 patients experience toxicities among the first 5 patients treated or if 7 or more patients experience toxicities among the first 10 patients.

Table 2. Stop accrual if the number of toxicities is greater than or equal to indicated (i.e., # patients with toxicities) among the number of patients evaluated

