# patients evaluated	# patients with toxicities	# patients evaluated	# patients with toxicities
5	5	45	22-45
10	7-10	50	24-50
15	9-15	55	26-55
20	11-20	60	28-60
25	14-25	65	30-65
30	16-30	70	32-70
35	18-35	75	34-78
40	20-40	80	Always stop with his many patients

Monitoring the response rate, based on the above assumptions will begin after 5 patients are treated, on an intent-to-treat basis (Table 3). For example, accrual will cease if 0 patients experience a response in the first 10 patients treated.

Table 3. Stop accrual if the number with CR is less than or equal to indicated (i.e., # patients with CR) among the number of patients evaluated							
# patients evaluated	10-20	25-30	35-40	45	50-55	60-65	70
# patients with CR	0	0-1	0-2	0-3	0-4	0-5	0-6

The probability of stopping the study early for low CRRs (i.e., 10%) was higher than 0.70 when toxicity rates were ranged from 20% to 40%. Probabilities of stopping early for high true toxicity rates (i.e., 40%) were 81% when the true CR rate was 10% and 45% when true CRR was 20%.

Table 4. Operating characteristics for simultaneous monitoring response and toxicity rates for patients treated				
True CRR	True Toxicity Rate	True Probability Vector (CRR/Tox, CRR/NoTox, NoCRR/Tox, NoCRR/NoTox)	Probability of Stopping	Average number of patients treated
10%	20%	(0.02, 0.08, 0.18, 0.72)	0.6960	44
10%	30%	(0.03, 0.07, 0.27, 0.63)	0.7076	43
10%	40%	(0.04, 0.06, 0.36, 0.54)	0.8054	36
20%	20%	(0.04, 0.16, 0.16, 0.64)	0.1346	71
20%	30%	(0.06, 0.14, 0.24, 0.56)	0.1676	69
20%	40%	(0.08, 0.12, 0.32, 0.48)	0.4462	57

30%	20%	(0.06, 0.24, 0.14, 0.56)	0.0309	78
30%	30%	(0.09, 0.21, 0.21, 0.49)	0.0679	76
30%	40%	(0.12, 0.18, 0.28, 0.42)	0.3798	61

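### Table 3 omits the 75-patient CR boundary that Table 4 was computed with, and two sentences in Section 11.2 misdescribe Table 4's stopping probabilities

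*Combined protocol and SAP*

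**What the plan says.** Section 11.2 of the combined protocol and SAP monitors CR and toxicity together with Bayesian rules.

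- **Priors.** For CR, "a beta (20, 80) and beta (0.4, 1.6) priors were assumed for the standard treatment response distribution" and the experimental response distribution respectively. For toxicity, "a beta (30, 70) and beta (0.6, 1.4) priors were assumed for the standard treatment toxicity rate" and the experimental toxicity rate respectively.
- **Cutoffs.** The CR rule stops when it is "unlikely (i.e., probability < 2.5%) that CR rate of the experimental treatment is 20"%. The toxicity rule stops when "excessive toxicity is highly probable (i.e., probability >97.5"%).
- **Looks.** "Assuming the minimum number of patients is 5, the maximum number of patients is 80 and the cohort size is 5". This puts the last interim look at 75 patients.
- **Boundaries.** Table 2 (toxicity) has an entry at 75 patients. Table 3, captioned "Stop accrual if the number with CR is less than or equal to indicated", ends at 70 patients with 0-6 CRs.
- **Operating characteristics.** The text says the probability of stopping at CR 10% "was higher than 0.70 when toxicity rates were ranged from 20% to 40"%. It continues: "Probabilities of stopping early for high true toxicity rates (i.e., 40%) were 81"% at CR 10% and 45% at CR 20%. Table 4 gives 0.6960, 0.7076 and 0.8054 at CR 10% for toxicity 20%, 30% and 40%, and 0.4462 at CR 20% with toxicity 40%.

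**The concern.** Three things do not line up. The looks run to 75 patients and Table 2 follows them, but Table 3 stops one look short. If Table 4 was computed with a CR boundary at 75, the printed rules do not have the printed operating characteristics. The 0.70 sentence disagrees with the first row of the table below it. And the 81% and 45% come straight after a sentence on stopping for low CR rates, so they read as protection given by the toxicity rule, although Table 4 describes both rules acting together.

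At stake are one decision and one impression. A team working from Table 3 would enrol the last five patients with 7 CRs among 75, where the stated criterion says to stop. A safety reader could take 81% as the chance that the toxicity rule detects a 40% toxicity rate, when Section 11.2 calls anything above 30% unacceptable.

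**Working it through.** **Inputs, all from Section 11.2.** CR priors Beta(20, 80) standard and Beta(0.4, 1.6) experimental; toxicity priors Beta(30, 70) and Beta(0.6, 1.4); cutoffs 0.025 and 0.975; looks at 5, 10, ..., 75; maximum 80; the joint probability vectors in Table 4.

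**Step 1. Boundaries.** After x CRs in n patients the experimental rate is Beta(0.4 + x, 1.6 + n − x). The rule stops if

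Pr(θE > θS | data) = ∫ fE(t) FS(t) dt < 0.025,

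where fE is the experimental posterior density and FS the Beta(20, 80) distribution function. Numerical integration returns every printed Table 3 entry. The lower limits of Table 2 also all match the toxicity criterion. At the look missing from Table 3:

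- 7 CRs in 75, Beta(7.4, 69.6): Pr = 0.0239 < 0.025, stop.
- 8 CRs in 75, Beta(8.4, 68.6): Pr = 0.0448, continue.

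The stated rule therefore has a boundary of 0-7 at 75 patients.

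**Step 2. Reproduce Table 4.** Stopping probabilities follow exactly by recursion on the joint count of CRs and toxicities, adding five patients at a time and removing the mass that meets either boundary. With 0-7 added at 75, all nine printed probabilities are recovered to four decimals: 0.6960, 0.7076, 0.8054; 0.1346, 0.1676, 0.4462; 0.0309, 0.0679, 0.3798. They are not all recovered with Table 3 as printed, nor with 0-6 at 75.

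**Step 3. Table 3 as printed.**

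| True CR | True toxicity | Table 4 | Printed Tables 2 and 3 | Difference |
|---|---|---|---|---|
| 10% | 20% | 0.6960 | 0.6591 | 0.0369 |
| 10% | 30% | 0.7076 | 0.6721 | 0.0355 |
| 10% | 40% | 0.8054 | 0.7818 | 0.0236 |
| 20% | 20% | 0.1346 | 0.1330 | 0.0016 |
| 20% | 30% | 0.1676 | 0.1661 | 0.0015 |
| 20% | 40% | 0.4462 | 0.4452 | 0.0010 |
| 30% | 20%, 30%, 40% | 0.0309, 0.0679, 0.3798 | the same | 0.0000 |

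A trial with 6 or fewer CRs at 70 has already stopped. The extra boundary therefore acts only on trials with exactly 7 CRs at 70 and none in the next five patients, and each such stop saves five patients. The effect on mean sample size is 5 × 0.0369 = 0.18, 5 × 0.0355 = 0.18 and 5 × 0.0236 = 0.12 patients in the CR 10% rows (43.84 against 44.03, 42.83 against 43.01, 36.47 against 36.59).

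**Step 4. The 0.70 sentence.** Against Table 4 it fails at 20% toxicity, by 0.7000 − 0.6960 = 0.0040. Against the printed boundaries it fails at 20% and 30% toxicity (0.659 and 0.672).

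**Step 5. What the 81% and 45% contain (with the 75-patient boundary).**

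- CR 10%, toxicity 40%: 0.5856 CR rule only + 0.1972 toxicity rule only + 0.0226 both at the same look = 0.8054. The CR-only share is 0.5856 / 0.8054 = 73%.
- CR 20%, toxicity 40%: 0.1207 + 0.3199 + 0.0056 = 0.4462. The CR-only share is 0.1207 / 0.4462 = 27%.

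With only the toxicity rule running, the probability of stopping is 0.361 at 40% toxicity, 0.040 at 30% and 0.002 at 20%. With only the CR rule running, it is 0.695 at CR 10% (0.658 without the 75-patient boundary).

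**The case against.** The priors, cutoff, cohort size and maximum are all in the text and fully determine 0-7 at 75, so Table 3 omits one entry of a rule that is otherwise specified. That stands. It also limits the harm: a stop at 75 spares at most five patients.

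A reader might infer that the stopping probabilities in Section 11.2 are wrong throughout, or that the trial lacks its stated futility property. The documents do not support this. Only the three CR 10% rows move materially, and the quoted 45% stands under the printed boundaries (0.4452). Nor do the documents say that staff apply Table 3 by hand. Section 11.1 describes web-based monitoring for OS only, and how the CR rule is run is not stated. A column lost when the PDF was read cannot be excluded either, although the header and value rows both end at 70.

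A reader might also infer that 81% and 45% are wrong numbers. They are not. The sentence can mean stopping when true toxicity is high, it gives a separate figure for each CR rate, and Table 4 is captioned as simultaneous monitoring. The CR 30%, toxicity 40% row (0.3798) even hints at the strength of the toxicity rule. What remains is that the sentence invites attribution to toxicity and that the 36% is not stated.

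Finally, 0.6960 rounds to 0.70, so against Table 4 the wording slip is tiny. The larger shortfall follows from the missing boundary and is not a separate error.

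**Conclusion.** The point holds in a limited form and is minor.

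- **Missing boundary.** Table 3 lacks the 0-7 entry at 75 patients that the stated criterion implies and Table 4 uses. Taken literally, Table 3 lowers stopping at CR 10% by 2.4 to 3.7 percentage points. It barely affects CR 20%, does not affect CR 30%, and changes mean sample size by under 0.2 patients.
- **The 0.70 claim.** Table 4 contradicts it at 20% toxicity, by 0.4 percentage points.
- **The 81% and 45%.** Both are correct as overall stopping probabilities. The wording misleads because most of the 81% is CR futility, while the toxicity rule alone stops about 36% of trials at 40% toxicity.

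This rests on the priors, cutoffs, looks and joint vectors as printed, and on Table 3 truly ending at 70 in the source document. The exact match of all nine Table 4 probabilities leaves little doubt about which boundaries were used.

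**What to change.** 1. Add an entry to Table 3: 75 patients, 0-7 CRs. If no CR look at 75 is intended, say so and recompute Table 4; its CR 10% rows then become 0.659, 0.672 and 0.782.
2. Replace the claim of more than 0.70 with the range 0.696 to 0.805.
3. Reword the 81% and 45% sentence as the overall probability of stopping under either rule when true toxicity is 40%. State beside it the probabilities for the toxicity rule alone: 0.2%, 4% and 36% at true toxicity 20%, 30% and 40%.
4. In the same edit, correct the upper limit of 78 printed in Table 2 for 75 patients, which exceeds the number evaluated.

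The cost is table and wording corrections only. Priors, cutoffs, sample size and Table 4 stay as they are if the 75-patient entry is added. The safety figures that a reader sees become less favourable once the toxicity rule is reported on its own.
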